## 2.2 ENDPOINTS

### 2.2.1 Primary Endpoint

The glucagon response to hypoglycaemia after a period of increased time in range using automated insulin delivery and a low carbohydrate diet compared with the glucagon response at baseline.

### 2.2.2 Secondary Endpoints

Treatment satisfaction, fear of hypoglycaemia and quality of life at baseline compared to endpoint using validated questionnaires. Changes in endogenous glucose production and glycerol kinetics as measured by stable isotope studies. The difference in time in range and QoL between participants using the HCL system and following the LCD and those using the HCL system alone will be compared.

## 3 STUDY DESIGN

This is a feasibility pilot study involving 24 participants with T1D. We aim to achieve improved glycaemic control using new generation Automated Insulin Delivery systems which consist of:

- Tandem t:slim X2 insulin pump
- Continuous glucose monitoring using the Dexcom G6
- Control IQ technology which uses an algorithm to adjust insulin delivery using CGM data

To reduce postprandial glucose excursions the intervention arm of this study will also follow a low carbohydrate diet (30-40g of carbohydrate per main meal portion).

Healthcare professionals who are trained in the use of these technologies will monitor patient data and implement pump setting changes as required during the study period in order to maximise TIR. Study staff will be able to obtain technical support from both Tandem and Dexcom throughout the trial period.

Participant's CGM data will be available to the study staff using Dexcom clarity which is a secure cloud based data storage system. Participant's Tandem t:2 slim X2 data will be available via the t:connect Diabetes Management Application, another secure cloud based data storage system, which participants will upload their pump data to.

Face-to-face visits will be at the Edinburgh Royal Infirmary. Each participant will be in the study for 9 months. Those in group 1 will be invited to take part in a 3-month

[figure not shown]
study extension phase where they will be converted to the study devices. Over this time their glucose data will be collected and at the end of the 3-months they will complete quality of life questionnaires.

The trial is expected to last for 14 months.

## Study Devices

### Dexcom G6 Continuous glucose monitor (CGM)

#### G6 components:

##### Display Device

This shows glucose information on a smart device, Dexcom receiver or both.

[figure not shown]
##### Applicator With Built-in Sensor

Using an easy-to-use applicator with one button insertion the sensor is inserted under the skin of the abdomen or hip. This sensor receives accurate glucose information from interstitial body cells.

##### Transmitter

This clips into the sensor and sends glucose information from the sensor to the display device. The system is water resistant.

#### How it works:

The G6 sends glucose readings, via Bluetooth, to the display device every 5 minutes. The sensor is changed every 10 days. There is no calibration required so no need to check fingerstick glucose routinely.

### Dexcom G6 Glucose Alarm/Alerts

The display device gives the user the power to customise an alert schedule. It alerts to;

- Low Glucose
- Urgent Low Glucose
- Urgent Low soon
- High glucose
- Rise rate
- Fall rate
- No readings

Urgent low soon alert provides a 20 minute warning of when the blood sugar is expected to be 3.1mmol/l or 56mg/dl so this can be avoided.

[figure not shown]
## Tandem t:2 slim X2 Insulin Pump

- The t:slim X2™ insulin pump is one of the smallest pumps available.
- 300 unit insulin cartridge.
- Rechargeable battery.
- Durable aluminium case.
- High-grade, shatter-resistant glass touchscreen.
- Customisable basal insulin rates.
- Integrated bolus calculator.

## T:2 slim X2 infusion sets.

Tandem provide a choice of insulin infusion sets. These are inserted every 3 days using an automated, intuitive application device.

Areas of the body suitable for infusion set insertion.

T:2 slim X2 insulin pump and infusion set.

### Control IQ

The t:2 slim X2 is an insulin pump that contains Control-IQ Technology. This is a third-generation closed-loop control system containing an algorithm that has been implemented in two mobile platforms (DiAs and inControl) and has been tested in 30 clinical trials by 450 adults and children with type 1 diabetes for over 280,000 hours of use to date.

This control algorithm provides the user with automated insulin correction boluses and a dedicated hypoglycaemia safety system that attenuates smoothly or discontinues insulin delivery using CGM and insulin-on-board information. It also gradually intensifies control overnight. Every five minutes Control-IQ receives CGM glucose data in order to inform insulin delivery. If glucose is in the target range, it delivers the insulin according to the user's settings. If out of range, it will give more or less insulin. The algorithm can use the CGM data to adjust insulin delivery based on the patients predicted blood glucose over the next 30 minutes.

In the closed-loop group of the recently published iDCL trial the median percentage of time Control IQ was in closed-loop mode was 90%, this was consistent throughout the 6 months (11).

Control IQ has FDA approval in the USA. December 2019. It launched in the UK in July 2020 after receiving a CE mark.

## 4 STUDY POPULATION

### 4.1 NUMBER OF PARTICIPANTS

Enrolment will proceed with the goal of having 24 participants enter the trial. The participants will be people with type 1 diabetes recruited from the NHS Lothian diabetes pump waiting list and type 1 diabetes clinic. Recruitment will be staggered with each participant entering the trial for a 9 month period. The trial is expected to last 14 months.

### 4.2 INCLUSION CRITERIA

- Participants with Type 1 diabetes with C-peptide levels less than 200pmol/L.
- Age 21-65.
- Type 1 diabetes for 5 years or more.
- HbA1c greater than or equal to 53 mol/mol.
- Normal renal function.
- Normal thyroid function.
- Willingness to monitor blood ketones daily.
- Use of freestyle libre device is permitted at study entry and may be continued in participants in group 1

### 4.3 EXCLUSION CRITERIA

- Current use of a non-approved closed loop / AID system or those on a predictive low glucose suspend insulin pump.
- Proliferative retinopathy
- Regular use of real time CGM in the preceding 3 months.
- History of Diabetic ketoacidosis in the preceding 6 months.
- Severe hypoglycaemic episode requiring external assistance in the preceding 6 months.
- Inability to safely use technology used in this study (e.g. impaired vision, memory or dexterity that prevents safe operation of CGM or insulin pump.)
- Inability to support the technology requirements for the study (e.g. unable to upload study device at home)
- History of Haemophilia, Cystic Fibrosis, pancreatic disease or complete pancreatectomy, ischaemic heart disease, cardiac arrhythmia, epilepsy or hypoglycaemia induced seizure
- History of severe reaction or allergy to adhesive necessary to this study.
- Unable to adhere to study timetable.
- Unable to give informed consent.
- Pregnancy or planning pregnancy. We will perform a pregnancy test on all eligible participants at baseline.
- Concurrent use of any non-insulin glucose-lowering agent (including GLP-1 agonists, Symlin, DPP-4 inhibitors, SGLT-2 inhibitors, sulfonylureas. These may lower insulin requirements and predispose to diabetic ketoacidosis.
- Concurrent use of medication that may affect blood glucose such as SSRIs
- A condition, which in the opinion of the investigator, would put the patient or study at risk

## 4.4 CO-ENROLMENT

Study staff will discuss with participants on a case-by-case basis if they are planning on enrolling in another study. The participant and study staff must consider the burden on the participant of being enrolled in more than one study. Any other study that a participant enrolled in would need to have no impact on their glycaemic control as this would potentially make the results from this study invalid.

# 5 PARTICIPANT SELECTION AND ENROLMENT

## 5.1 IDENTIFYING PARTICIPANTS

Study staff, who are part of the diabetes care team in NHS Lothian, will identify potential participants from the type 1 diabetes clinic and the insulin pump waiting list.

Electronic health records, Trakcare and SCI Diabetes, of potential participants will be screened for any exclusion criteria. If no exclusion criteria are identified study staff will write to the potential participant inviting them to contact the research team if they would like to know more about the study. Potential participants will be able to contact study staff by post or email to arrange a telephone call to discuss the study. If after discussion with study staff on the phone potential participants would like to know more about the study they will be sent the participant information leaflet and the consent form by post to review.

## 5.2 CONSENTING PARTICIPANTS

Before completing any procedures or collecting any data that are not part of usual care written informed consent will be obtained. This will be obtained at the screening visit.

The study protocol will be discussed with the potential participant by study staff over the phone. They will be sent the Patient Information Leaflet and Informed Consent Form to read and will be encouraged to discuss the study with family members, study staff and their personal doctors before deciding whether to participate in the study. Participants will be given a minimum of 5 days and a maximum of 14 days to consider taking part in the study. The participant will be given contact details for study staff should they wish to ask further questions during this 14 day period. If study staff are not contacted by the potential participant within this 14 day period they will follow-up with a telephone call.

### 5.2.1 Withdrawal of Study Participants

Participants are free to withdraw from the study at any point or a participant can be withdrawn by the Investigator. If withdrawal occurs, the primary reason for withdrawal will be documented in the participant's case report form, if possible. The participant will have the option of withdrawal from:

- (i) all aspects of the trial but continued use of data collected up to that point . To safeguard rights, the minimum personally-identifiable information possible will be collected.
- (ii) Participants can also ask for all data previously collected about them to be removed and not used in analysis
- (iii) Participants do not have to give a reason for withdrawal from the trial

## 6 STUDY ASSESSMENTS

### 6.1 STUDY ASSESSMENTS

#### Study Visit 1: Eligibility Assessment

After informed consent has been signed the potential participant will be evaluated for study eligibility. This will be done through the elicitation of a medical history, performance of a physical examination by study staff and local laboratory testing if needed to screen for exclusionary medical conditions.

The following data will be collected:

- Inclusion and exclusion criteria assessment.
- Demographics (date of birth, sex)
- Contact information (retained at the site and not entered into study database)
- Medical history
- Concomitant medications
- Pregnancy test if applicable
- HbA1c blood test
- Urine sample for albumin:creatinine ratio
- Physical examination to include: Weight, height, BMI, vital signs including measurement of blood pressure and heart rate
- Retinal screening will be arranged if this has not occurred in the previous 6 months
- Modified Clark and Gold score

At the end of this visit participants will be given the following questionnaires:

1. EQ5D
2. Fear of Hypoglycaemic Scale
3. Hypoglycaemic Confidence
4. Diabetes Technology Attitudes
5. Diabetes Specific Emotional Distress (DDS-1)
6. Diabetes Treatment Satisfaction Questionnaire

They can either complete these at the time of the visit or complete at home and return to study staff at the following visit. A stamped addressed envelope will be provided to return the forms.

#### Randomisation

We will perform stratified random sampling according to age, gender and BMI. We will then provide envelopes to randomly assign final members from the various strata,

these envelopes will be kept in a secure, locked unit within in the clinical research facility. This technique ensures that observations from all relevant strata are included in the sample. by stratified sampling to match for: age, gender and BMI. They will be assigned to one of two groups:

- Group 1: Controls: standard diabetes care with blinded CGM (Dexcom G6) on three occasions lasting 20 days. All will be invited to a 3-month study extension phase where they will be converted to the study devices.
- Group 2: New-generation AIDs (t:slim X2 insulin pump with Control-IQ technology) with CGM (Dexcom G6) and a low carbohydrate diet (30-40g of carbohydrate per main meal portion). They will also have a 20-day period of blinded CGM (Dexcom G6) at baseline

Amendment: 28/09/22: Recruitment and retention to group 1 has been challenging with potential participants not wanting to engage with the study if allocated to group 1. This has led to unbalanced study groups. Currently there are 11 participants in group 2 and only 3 participants in group 1 (with a further 2 participants previously recruited but choosing to leave the study early). In order to balance groups from now on participants will be approached to take part in the study and informed up-front that they will be allocated to group 1.

Dexcom G6 clinical supplies, technical and software assistance will all be provided by Dexcom (see letter of support: Dr [name], Senior US Medical Director, Dexcom).

Participants will be asked to choose an envelope at random at the end of the screening visit which will allocate them to a group. At this time arrangements for subsequent visits will be made. We will send those randomised to group 2 training materials for the insulin pump and CGM. Participants will be allocated to a group within 1 week of the screening visit. This will change in version 8 of the protocol (28/09/22), from this point participants will only be recruited to the control group (group 1) and not randomised.

### Visit 2- Baseline Data

All participants will attend for a second visit at ERICRF or ERI outpatient department. Participants will be fitted with a Dexcom G6 CGM. They will use this, blinded, for twenty days to gain experience in its insertion and for the research team to gain baseline data on glycaemic control. They will be required to insert two CGM devices to cover this 20 day period with support from study staff as required. If during this time the CGM device falls off or is faulty a replacement CGM device will be provided to the participant if less than 14 days of data has been collected. As participant's will not be able to view their CGM data during this time they will have to continue to monitor their own blood glucose as they would do normally.

All participants will be asked to complete a 7-day food diary during this period of blinded CGM. They will be asked to include 5 week days and 2 weekend days in the diary. This diary can take the form of a paper diary provided by study staff or participants can use a mobile phone application if they prefer. They will be asked to document food consumed and their insulin doses. They can return this to study staff

by post or at the next visit. A stamped addressed envelope will be provided if returning the diary by post.

### Study Visit 3 (Group 2 only)

Participants randomised to Group 2 will attend the ERI to meet study staff, be fitted with their insulin pump and CGM device. This will take place after the 20-day period of blinded CGM monitoring. They will return the completed food diary at this visit. Participants in this group will be given training in the use of the pump that is in-line with what is received by NHS patients commencing on insulin pump therapy. This will require the participant to complete online training modules prior to attending this visit. They will also undergo a virtual or face-to-face pump start session with study staff and a training representative from the pump distributor. At this training session their knowledge of the pump will be checked against a standard checklist and we will ensure that the training modules have been completed. They will also be provided with written materials on the use of the pump and the algorithm which are produced by the pump manufacturer. Ongoing support on the use of the pump will be provided by study staff throughout the study period as is required by the participant, this can be via telephone contact for face-to-face if required. The pump manufacturer also has an online presence, including training and troubleshooting videos that can be freely accessed by participants (Tandem YouTube channel:

<https://www.youtube.com/channel/UCBpeluXQrQC-SGGooyxOhKA> and Dexcom online training resources: <https://www.dexcom.com/en-GB/training-resources>).

Whilst on an insulin pump the participant will change their own insertion site every three days. This is routine in insulin pump use and is a marked reduction in injections when compared with insulin pens and needles, which is often done five to six times daily. They will also receive advice from the study team with respect to the low carbohydrate diet plans and management of insulin doses for their carbohydrate portions. This advice will be informed by the food diary completed by the participant. Participants in this group will be given blood ketone testing sticks and asked to do these tests daily. If blood ketones are greater than 1.5 mmol/L they will be asked to contact the health care professionals involved in the study or the out of hours care team. Participants will be given a paper record for them to record their ketone readings. This will change from protocol version 8 (28/09/22), from this point routine ketone monitoring will no longer be required. Participants will only be asked to monitor ketones as per standard diabetes management guidelines.

### Study Run- in and Visit 4 (by telephone)

Participants in Group 2 will enter a maximum 2-week study run in period to adjust to their new equipment. Over this time the participants will be unblinded to their CGM data. The length of the run-in period will be determined on an individual basis after discussion between the participant and the investigators and will be based on the participant's previous experience with and confidence in using the technology.

Data will be monitored by the study staff and participants will be able to contact study staff by telephone or email to discuss any issues. At the end of this run-in period participants will meet with study staff either virtually or in person if they prefer this to assess:

1. Compliance with the use of the study devices

2. Any skin reaction in areas where a CGM sensor or pump set site was worn
3. Proficiency with the CGM and insulin pump technology by reviewing the individual items listed on the pump training checklist
4. Eligibility to continue to in the trial, which requires:
  - a. CGM readings being obtained on at least 11 of the previous 14 days- if completing the full 14-day run in period
  - b. Successful use of the pump every day

Additional visits and phone contacts for further training are at investigator discretion.

The pump settings (insulin: carbohydrate ratios, basal rates and insulin sensitivity) will be reviewed and optimised as appropriate based on the participant's blood glucose readings over the run-in period.

#### Study Visit 5: Hypoglycaemic Clamp Study 1

All Participants will attend the ERICRF, group 2 after the 2-week run-in period, for the first hypoglycaemic clamp study. This technique is safe and is considered, worldwide, as the gold standard approach in the assessment of hypoglycaemia (15-17). The clamp study will last for 5-6 hours. Blood glucose data for the preceding 24 hours will be reviewed prior to the study and if there have been any hypoglycaemic episodes the clamp study will be postponed.

During the clamp study the participant's blood glucose will be lowered in three steps to 2.5mmol/l.

In the 48 hours preceding the study participants will be asked to avoid moderate/high intensity exercise and any medication that may affect blood glucose such as: salicylates and quinolone antibiotics.

In the 24 hours preceding the study participants will be asked to do the following:

- Avoid alcohol and caffeine
- Consume a moderate carbohydrate (40-60g) evening meal the night before
- Fast for at least 8 hours before presenting to the clinical research facility at 07:00 (participant can continue to consume water as required)
- Avoid hypoglycaemia- the study will be postponed if the blood glucose is <3mmol/l for >20 minutes
- If on basal/bolus or open loop pump system to reduce their basal insulin the night before by 20%
- If on a closed loop system to place the pump on exercise settings the morning of testing

The clamp study will be rescheduled if the participant has donated blood in the preceding 12 weeks if male and the preceding 16 weeks if female.

When participants arrive in the ERICRF they will have anthropological measurements taken to calculate their infusion rates accurately. They will also have a pregnancy test if applicable.

Two peripheral intravenous cannulas will be inserted. The first of these will be in the nondominant hand which will then be placed in a heated box at 55°C to aterialise venous blood. This will be used for blood sampling during the study. The second cannula will be inserted an antecubital fossa vein for the infusions. At the time of cannula insertion baseline bloods will be obtained for: glucose, glycerol, D2 Glucose, D5 Glycerol, Free Fatty Acids, lipid profile, insulin, glucagon, cortisol, adrenaline and noradrenaline. Note that bloods for D2-Glucose and D5-Glycerol will only be taken when the investigators have received supply of the isotopes. There is currently a delay in this supply and the investigators anticipate receiving the isotopes in January 2022. Clamp studies carried out before receipt of the isotopes will not have these samples taken.

### *Stable Isotope Studies*

Endogenous glucose production (EGP) and glycerol kinetics will be further assessed by infusion of the stable isotopes D2 Glucose and D5 Glycerol. This is a safe method for assessing EGP in humans (18, 19). The isotopes will be supplied by Tayside Pharmaceuticals ([name]). There are supply issues with the D5-glycerol but it is important that study visits are allowed to continue so that participants can progress through the 8 months of the study. Not using the D5-glycerol will not impact on the primary outcome of the study. The D5-glycerol supply issues will continue for the remainder of the study due to there being less raw material available from the supplier. This means that supply of the D5-glycerol will be intermittent and unpredictable for the remainder of the study. Visits that take place when D5-glycerol is available will be completed as described below. Visits taking place when D5-glycerol is not available will continue without using the D5-glycerol. The D5-glycerol is infused alongside the D2-glucose from the same infusion bag. So that the process for making this infusion remains unchanged the D5-glycerol will be replaced with 0.9% Sodium Chloride, which will not impact on the participant or the study results. Participants impacted by this change will be asked to sign another consent form.

This will involve:

1. A priming dose:
  - a. D2 Glucose: 26.4 micromol/kg
  - b. D5 Glycerol: 2 micromol/kg (if available)
2. A continuous infusion:
  - a. D2 Glucose: 0.5micromol/kg/minute for the remainder of the clamp study
  - b. D5 Glycerol: 0.1micromol/kg/minute for the remainder of the clamp study (if available)

The continuous infusion of each isotope will run for 90 minutes before the clamp study is commenced. During this time blood samples will be drawn for Glucose, Glycerol, D2 Glucose and D5 Glycerol (if being infused) on three occasions.

If the participant's blood glucose is  $>7\text{mmol/l}$  at the start of the study they will begin a priming infusion of Novorapid insulin  $0.3\text{U/ml}$  at  $50\text{ml/hour}$  until the blood glucose is  $<7\text{mmol/l}$  but  $>5\text{mmol/l}$ . Once blood glucose is  $<7\text{mmol/l}$  a basal insulin infusion will run at  $6\text{mU/m}^2/\text{min}$  until the start of the clamp study to maintain blood glucose in the euglycaemic range.

Insulin infusion rates will be calculated using the participants body surface area, which avoids overdosing insulin in overweight participants. The body surface area will be calculated using the formula:

$$\text{BSA (m}^2\text{)} = \sqrt{(\text{height (cm)} \times \text{weight (kg)}) / 3600} \quad (20)$$

After the isotopes have been infused for 90 minutes the insulin infusion will be increased to  $60\text{mU/m}^2/\text{min}$ . At the same time a variable rate 20% Dextrose infusion will also be commenced. The rate of this will be adjusted as required to obtain the desired blood glucose nadir.

We will have three blood glucose plateaus during the clamp study each lasting for 40 minutes:  $5\text{mmol/l}$ ,  $3\text{mmol/l}$  and  $2.5\text{mmol/l}$ . Throughout the clamp study blood glucose will be monitored every 5 minutes using near-patient testing and the participant will remain blinded to their blood glucose level. During each plateau blood will be drawn on 3 occasions at 10-minute intervals for: insulin, cortisol, adrenaline, noradrenaline, glucagon, glucose, glycerol, free fatty acids and the stable isotopes.

During the clamp the following additional tests will be carried out:

[figure not shown]
- Physiological measurements: Blood pressure and heart rate every 10 minutes.
- Symptoms scoring: Participants will rate symptoms at set intervals during hypoglycaemia. Symptoms will be scored on a validated questionnaire, The Edinburgh Hypoglycaemia Scale, scoring from 1 (not at all) to 7 (very severe) on a visual analogue scale. At any point participants may stop the test if symptoms are intolerable.
- Cognitive Function Tests: Psychometric tests known to be sensitive to hypoglycaemia will be applied at set time intervals during hypoglycaemia: Trail Making Test, Digit Span Test, Digit Symbol Substitution Test and Four Choice Reaction Time Test.

At the end of the study the participants will be examined and assessed to ensure they have fully recovered from the clamp. They will be given lunch consisting of at least  $60\text{g}$  of carbohydrate and post clamp advice. They may leave the CRF when blood glucose is stable above  $5\text{mmol/l}$ .

In total we will take not more than  $300\text{ml}$  of blood during the clamp study. The blood samples will be stored in a secure and monitored environment and will be disposed of according to the Human Tissue Authority's code of practice after a period of 5 years. The samples will be centrifuged before being frozen at  $-80$  degrees Celsius. Serum samples will be allowed to clot at room temperature before centrifugation.

[figure not shown]
At the beginning and end of the clamp study a sample will be taken from the infusates to confirm the isotope concentration in these. These samples will be frozen until analysis.

Figure 1: Hypoglycaemic Clamp Study with stable isotopes

Note in visits where the D5-glycerol is not available on the D2-glucose will be infused.

Figure 2: Hypoglycaemic Clamp Study without stable isotopes

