Protocol Synopsis	
After consent eligibility will be assessed. The trial will consist of 3 phases:
 
Phase 1: Baseline data. All participants will complete 20 days of blinded CGM with Dexcom G6
 
Phase 2: Study Run in. Group 2 will have 2 weeks using the t:slim X2 pump with Control IQ technology and the Dexcom G6 CGM unblinded.
 
Phase 3: Study. 8 months. Group 1 will continue routine care as pre-study. They will undergo two periods of blinded Dexcom G6 CGM monitoring each lasting 20 days. Group 2 will continue on their allocated devices and LCD with close monitoring by the study team to ensure TIR is maximised. Both groups will undergo a hyperinsulinaemic hypoglycaemic clamp study at 0 and 8 months. Group 1 will be invited to take part in a 3 month study extension phase where they are converted to the study devices and complete quality of life questionnaires.

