#### 2.1.2 Secondary Objectives

- Has the quality of life (QoL) improved with improved blood sugar control?
- Are there fewer hypoglycaemic episodes?
- Is there a lower burden of diabetes care?
- Has the fear of Hypoglycaemia changed as a result of using this technology?
- Has satisfaction with their diabetes treatment improved as a result of using this technology?
- Is there an improvement in HbA1c using this technology?
- Endogenous glucose production and glycerol kinetics as measured by stable isotope studies (glycerol isotope will be used when supply is available)
- Is there a similar improvement in TIR between participants using the HCL system and following a LCD and those using the HCL system and following their pre-study diet

- Is there a difference in QoL between participants using the HCL system and following a LCD and those using the HCL system and following their pre-study diet

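### D5-glycerol is allotted visit by visit with nothing linking a participant's two clamps, so some infusions can yield no 0-to-8-month change in glycerol kinetics

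*Combined protocol and SAP*

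**What the plan says.** Section 2.2.2 lists among the secondary endpoints: "Changes in endogenous glucose production and glycerol kinetics as measured by stable isotope studies". The Protocol Synopsis sets the measurement occasions: "Both groups will undergo a hyperinsulinaemic hypoglycaemic clamp study at 0 and 8 months".

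The Stable Isotope Studies text in section 6.1 explains that raw material is short and that "supply of the D5-glycerol will be intermittent and unpredictable for the remainder of the study". Its rule has two halves: "Visits that take place when D5-glycerol is available will be completed as described below", and "Visits taking place when D5-glycerol is not available will continue without using the D5-glycerol". In the second case saline replaces the tracer in the infusion bag. Section 2.1.2 repeats the condition: "glycerol isotope will be used when supply is available". The same text says that going without D5-glycerol leaves the primary outcome untouched; it does not discuss the effect on the glycerol endpoint.

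For both isotopes, the description of Study Visit 5 adds: "Clamp studies carried out before receipt of the isotopes will not have these samples taken".

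No passage links a participant's second clamp to what was infused at the first, sets a target number of pairs, or says how a participant with the tracer at one clamp only is analysed. Section 9.2 uses the isotopes' rate of appearance as a marker of endogenous glucose production. It does not mention glycerol kinetics or missing tracer.

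**The concern.** Taking the two clamps as the occasions for the change, a participant contributes an observed change in glycerol kinetics only if D5-glycerol was infused at both, 8 months apart. The rule looks only at the visit in hand. It can send scarce tracer to the second clamp of someone who had none at the first while another participant, who did have it at the first, goes without.

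At stake is the number of participants who can inform one secondary endpoint in a study of 24. Infusions that do not form a pair expose people to the tracer and use limited stock without adding to the observed change. The shortage was known and expected to last to the end of the study, so an order of priority could have been written into the rule.

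**Working it through.** **Inputs from the documents.**
- Participants: 24 (section 3, "This is a feasibility pilot study involving 24 participants with T1D").
- Clamps: 2 each (Protocol Synopsis), so 2 × 24 = 48 clamps and at most 24 pairs.

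**Inputs not in the documents.** The chance that D5-glycerol is available at a clamp (p), the number of doses, shelf life, and the number of clamps done before any isotope arrived. The plan gives no figure for expected infusions or pairs, so there is none to reproduce. Section 9.1 bases the 24 on similarity to an earlier study, without a power calculation.

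**Base case.** Assume availability is independent at each clamp with probability p, no withdrawals, and no one barred from a baseline infusion.
- Expected infusions = 48p
- Expected pairs under the current rule = 24p²
- Unpaired infusions = 48p − 2 × 24p² = 48p(1 − p), a share 1 − p of all infusions
- Ceiling on pairs if the same doses all went to people at both clamps = 48p / 2 = 24p

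| p (assumed) | Infusions | Pairs, current rule | Unpaired infusions | Share unpaired | Ceiling on pairs |
|---|---|---|---|---|---|
| 0.25 | 12 | 1.5 | 9 | 75% | 6 |
| 0.50 | 24 | 6 | 12 | 50% | 12 |
| 0.75 | 36 | 13.5 | 9 | 25% | 18 |
| 0.90 | 43.2 | 19.44 | 4.32 | 10% | 21.6 |

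At p = 0.50, with the same SD of change, the standard error of the mean change with 6 pairs is √(12/6) = 1.41 times that with 12.

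**Fixed number of doses.** If K doses fall at random on the 48 clamps, expected pairs = 24 × K(K − 1)/(48 × 47). For K = 24 this is 24 × 24 × 23/2256 = 5.87 against a maximum of 12, or 51% unpaired. The result barely moves.

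**Correlation between a participant's two visits.** With correlation r, pairs = 24[p² + r·p(1 − p)], so the share unpaired is (1 − p)(1 − r). At p = 0.50: r = 0.3 gives 35%, r = 0.6 gives 20%, r = −0.3 gives 65%.

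**How firm the ceiling is.** It is an upper bound, for three reasons.
- It needs doses that can be kept, or visits that can be moved to meet supply. If neither is possible, each visit's availability is set from outside, an order of priority has nothing to act on, and expected pairs stay at 24p².
- Participants whose first clamp came before the isotopes arrived can never form a pair. If there were 8 (an assumption), at most 24 − 8 = 16 pairs are possible, below the 18 shown for p = 0.75.
- Withdrawals reduce it. At the 28/09/22 amendment (section 6.1, Randomisation), 2 of the 3 + 2 = 5 Group 1 recruits had left early.

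**The case against.** The strongest reply is that this is one tracer for one secondary endpoint in a feasibility pilot. The constraint is disclosed, visits keep moving, a substitute infusion and fresh consent are provided, and the primary outcome is untouched. All of that stands and limits the weight of the point. It does not explain why stock that is limited should go to a visit that cannot complete a pair ahead of one that can.

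It can also be said that section 2.2.2 names no time points for the isotopes, that section 2.1.2 speaks of glycerol kinetics without restricting it to change, and that samples are drawn at three glucose plateaus within each clamp. This stands in part. A reader might infer that a single infusion is useless, and the documents do not support that: one-clamp data could describe the groups at that time point. But change between the two clamps is the natural reading of the endpoint, and no one-clamp analysis is planned.

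Finally, if the tracer cannot be stored and visits cannot be timed to supply, an order of priority recovers nothing. That is correct, and the documents do not settle it.

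**Conclusion.** The point holds, as a modest improvement to the rule for one secondary endpoint. D5-glycerol is allotted by visit, the endpoint is a change, and nothing connects a participant's two clamps. For an assumed availability of 0.75 down to 0.25, independent between visits, about 25% to 75% of infusions would be unpaired. The share is smaller with higher availability (10% at 0.90) or positive correlation. How much of this can be recovered depends on storage and scheduling, on which the documents are silent.

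Three stronger readings are tempting and should not be drawn.
- That half or more of the attainable pairs are lost. Under independence this needs p of 0.50 or less, and no availability rate is given.
- That D2-glucose pairs have already been lost. The text says what happens to clamps done before the isotopes arrive; it does not say that any were.
- That the D5-glycerol loss favours one group. Recruits from version 8 of the protocol are all Group 1, but the shortage runs to the end of the study, so late controls face it too.

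**What to change.** Amend the Stable Isotope Studies text so that, when D5-glycerol stock is limited, participants who received it at clamp 1 have first call on it for clamp 2. Any remaining stock is used at other visits as now.

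In sections 2.2.2 and 9.2, state that the change endpoints rest on participants with the same tracer at both clamps. Report their number per group, separately for D5-glycerol and D2-glucose. Use one-clamp data only in a separate between-group description at that time point.

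The cost is a short paragraph and a stock check before each clamp, with no extra tracer, visits or samples. The downside is that a few doses may be held for participants who then withdraw, or may expire. The reporting change is worth making even if stock cannot be held.

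Stricter rules are not recommended. Starting the tracer only when a second dose is reserved could strand doses. Withholding it at clamp 2 from everyone without a clamp 1 infusion would discard usable 8-month data.
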